- Women with IC/BPS who have a score of ≥ 6 on either index (problem or symptom index) of the O'Leary-Sant questionnaire who have selected bladder instillations as part of their IC/BPS treatment
- Suitability for follow-up

Exclusion Criteria:

- Contraindications to the ingredients used in the bladder instillations
 - In particular: allergy to ingredients
 - Diagnosis of idiopathic thrombocytopenic purpura
- Does not desire to undergo bladder instillation therapy or unwilling to undergo bladder instillation therapy on schedule mandated by study
- Have a known alternative diagnosis explaining bladder pain symptoms that would preclude the diagnosis of IC/BPS (e.g. radiation cystitis, active urinary tract infection with bacteria or fungus treated within last 2 weeks or diagnosed at index visit, bladder injury or trauma within the last 30 days)
- Inability to speak or read English
- Bladder instillation within the past 4 weeks

Study Title: Randomized controlled trial comparing two different bladder instillation treatments for interstitial cystitis/bladder pain syndrome.

Interventions:

Eligible patients will be randomized by a research statistician to one of two possible interventions:

1. Bladder instillation with Kenalog
2. Bladder instillation without Kenalog

The randomization sequence, generated by a statistician that is uninvolved in patient recruitment, will be in randomly alternating block sizes of 6-10 with a 1:1 distribution in each block. The sequence will be attached by a research medical assistant, also uninvolved in patient selection and recruitment, to the numbering of otherwise unmarked, identical syringes containing either a bladder instillation mixture with Kenalog or a mixture without Kenalog. The appearance of the syringes will be identical in every way except for the patient number on the labelling. The study investigators recruiting, treating, or assessing the patient during the study will not be aware of the patient's randomization, and the randomization sequence will not be opened until the last patient is through with the study unless an adverse event mandates.

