All study bladder instillation mixture will be drawn up in syringes, randomized, and dispensed (given to provider) by one of the medical assistants. The providers will be blinded to the study mixture and will perform the bladder instillations. The bladder instillation ingredients will be prepared in a standardized fashion by a trained medical assistant. The patients will undergo bladder instillations using a standardized technique by a physician or nurse practitioner. The medical practitioner will swab the external urethral meatus with betadine (or other appropriate cleansing agent if patient has an iodine allergy) and then instill approximately 5 mL of 1% viscous lidocaine in the urethra, letting the viscous lidocaine sit for 1 to 10 minutes. A pediatric (8 French) straight-tip catheter will be inserted to drain the bladder and collect a urine specimen for culture if indicated. After the bladder is drained, the bladder will be instilled with either a mixture of triamcinolone acetonide (1 vial, 40 milligrams (mg)/1 milliliters (mL)), heparin (10,000 units), 2% viscous lidocaine (10 mL), 8.4% sodium bicarbonate (15 mL of 1 mEq/mL), and 0.5% bupivacaine (10 mL of 5 mg/mL). After the instillation, the women will lay supine or move from supine to lateral positions intermittently for 20-30 minutes. They will then urinate the instillation. If a patient has previously demonstrated the ability to urinate without difficulty following an instillation, she may depart the office after 20-30 min and urinate the instillation in a more private, non-office setting.

If patients have a reaction to the bladder instillation or desire to stop the instillations, they may do so. Participants will be permitted to obtain any relevant concomitant care and interventions during the trial.

Outcomes

All outcome measures will be collected at 3 weeks into the bladder instillation schedule and again at the completion of the bladder instillations (6 weeks into study participation).

Study Title: Randomized controlled trial comparing two different bladder instillation treatments for interstitial cystitis/bladder pain syndrome.

Primary Outcome:

1. Treatment response as measured by the score of the O'Leary-Sant questionnaire [16,17] as compared between study groups at completion of the bladder instillations.

Secondary Outcomes:

1. O'Leary-Sant subscores (problem and symptom index) at the completion of treatment

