Participants will be enrolled from the FPMRS clinics as noted above, at the time when a diagnosis of ICBPS is established (score ≥ 6 on either the symptom or the problem index of the O'Leary-Sant questionnaire) and the patient has expressed desire for bladder instillations as a therapy for this disorder. Recruited subjects will be given a sequential study ID number (SIDN) at the time of their informed consent, which cannot be changed or altered throughout their course in the study.

Methods: Assignment of interventions

Allocation:

Sequence generation

Study Title: Randomized controlled trial comparing two different bladder instillation treatments for interstitial cystitis/bladder pain syndrome.

The randomization schedule will be created by an uninvolved statistician (not involved with study enrollment or data collection) using a random permuted block design (randomly varying from 6-10 patients per block with a 1:1 distribution within each block) to reduce predictability of a random sequence. The statistician will provide the sequence to the medical assistant, who will correspond this to expected study ID numbers (SIDNs) of future subjects in the given sequence. Study medications and packaging in agreement with this preset sequence will be made prior to the recruitment of that subject.

Allocation concealment mechanism

The allocation concealment will be in the form of randomization, where only the biostatistician creating the allocation sequence and the medical assistant creating the study bladder instillation mixtures and are aware of the patient allocation. As both of these parties are uninvolved in patient eligibility determination, recruitment, and direct patient care and follow up, this will maintain allocation concealment from the investigators. Under no circumstances will the planned allocation for the patient be known at the time of recruitment.

Implementation

The investigators will enroll and consent eligible participants. The participants will be given their study number. This number will be tied to a bladder instillation mixture known to the medical assistant who will prepare the mixture but not to the study investigators or participants. This number serves as the participant's allocation.

Blinding (masking)

Patients and investigators will be blinded to treatment allocation, so this is a “double-blind” randomized, controlled trial.

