All identifying information and data collected during the course of this study will be kept secure and strictly confidential. All data will be stored electronically on a password protected, encrypted laptop in the possession of the study investigator. Risks for breaches of confidentiality will be minimized by entering data from the medical record to a password protected, encrypted computer database which will have limited access to the PI.

The patient's unique study ID will be used for storage, analysis and publication.

Paper data collections forms will be utilized and data will be entered from the paper data form by a study investigator into either a RedCap database or an encrypted, password protected laptop or computer Excel database. These data forms will be housed in a locked file cabinet in the Division of Female Pelvic Medicine and Reconstruction office in a locked cabinet with restricted access.

Data Analysis and Statistical Methods:

The data will be analyzed in consultation with a department-committed biostatistician utilizing SPSS statistical software. Categorical variables (e.g. 'yes" to certain questions on the PFDI) will be compared using chi-square tests (or Fisher's exact test when appropriate). Continuous variables (such as primary outcome) will be compared using t-tests, and changes in continuous outcomes over time (e.g. change from baseline to 8-week O'Leary-Sant score) will be compared with paired t-tests. A regression analysis will be performed to determine the impact of various relevant cofactors (e.g. patient age, presence of other chronic disorders, level of OAB symptoms) on the relationship between group assignment and treatment outcomes.

We will perform an intention-to-treat analysis by the assigned study groups for the initial analysis, comparing women who followed up at the completion of the study (6-week outcomes) between the study groups (bladder instillations with and without Kenalog) as

Study Title: Randomized controlled trial comparing two different bladder instillation treatments for interstitial cystitis/bladder pain syndrome.
assigned. We will also perform a per-protocol analysis, comparing women in the bladder instillation with Kenalog who had at least 4 bladder instillation treatments to the group that had bladder instillations without Kenalog. Lastly, we will perform two types of sensitivity analysis:

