The investigators will take great care to protect and secure all study data collected for this study. Risks for breaches of confidentiality will be minimized by entering data from the medical record or paper data collection forms to a password protected, encrypted computer database which will have limited access to the PI, Co-PIs, and sub-investigators.

Study Title: Randomized controlled trial comparing two different bladder instillation treatments for interstitial cystitis/bladder pain syndrome.

Personal identifiers (name, DOB, contact information for patient and an emergency contact person, and social security number) will be collected and retained in the event of need to contact patients with clarification of questionnaire responses, urgent study alerts, or early termination of the study by the investigators. However, all study information will be completely de-identified by using a study code or number instead of identifiers for the purposes of data analysis and reporting.

Data will be de-identified as soon as is feasible without compromising the study. Data will be stored as an encrypted file on a password protected laptop computer or password protected shared U of L drives, ULP share point server or secure hospital database. Data will NOT be stored on a ‘cloud’ type server per HIPAA regulations.

A de-identified Excel spreadsheet will be provided to the statistician for statistical analysis. Statistical consultants on this study will only work with totally de-identified data and will never see patient identifying information, patient images, or patient medical records.

The protected health information gathered for this study will be destroyed as soon as is feasible and will not be reused or disclosed to any other person or entity, except as required by law. The Excel “key” spreadsheet listing Research ID #, name, DOB, contact information for patient and emergency contact, and SSN will be kept distinct from the remainder of the study information as a means to contact patients or identify the patient as needed for safety, medical care, or study-wide alerts. As soon as all data have been collected and there is no further need to return to a subject’s contact information and identifying information, the Excel key(s) linking name, DOB, contact information, and SSN to study ID numbers (SIDNs) will be destroyed.

Declaration of interests:

The PI does not have any financial disclosures or competing interests for the overall trial.

Access to data:

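### The randomisation sequence may be opened when the last patient finishes rather than at database lock, so remaining data entry, clarification of answers and secondary analysis choices may be made with the arms known

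*Combined protocol and SAP*

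**What the plan says.** Only one sentence in the protocol sets a time for opening the code. It is in Interventions: "the randomization sequence will not be opened until the last patient is through with the study unless an adverse event mandates". The sentence before the colonised rule in the same paragraph limits the investigators' masking to the conduct phase: "The study investigators recruiting, treating, or assessing the patient during the study will not be aware of the patient's randomization". Blinding (masking) adds, without an end point, "Patients and investigators will be blinded to treatment allocation, so this is a “double-blind” randomized, controlled trial". Under Allocation concealment mechanism, "only the biostatistician creating the allocation sequence and the medical assistant creating the study bladder instillation mixtures and are aware of the patient allocation".

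The primary outcome is "Treatment response as measured by the score of the O'Leary-Sant questionnaire", compared between groups at completion of the instillations. Data collection methods has the women fill in the questionnaires themselves, on paper, the last set at the sixth instillation.

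After that, Data Handling/Storage says that "data will be entered from the paper data form by a study investigator", with no deadline. Access to data names one investigator who does data entry and management, and makes that person the only holder of the key linking study numbers to women. Under Confidentiality, identifiers are "retained in the event of need to contact patients with clarification of questionnaire responses", again with no cut-off. Data Analysis and Statistical Methods says "A regression analysis will be performed to determine the impact of various relevant cofactors" and gives the cofactors as examples only. The statistician receives a de-identified spreadsheet; whether the arm is masked is not stated.

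**The concern.** In a double-blind trial the code normally stays closed until nothing that depends on judgement remains to be done to the data. Here the trigger is the last patient's completion, which can come before the data are final. Once the sequence is open, the study number on a form identifies the arm, and the key identifies the woman. The investigator who enters the data has both.

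Three activities are then unprotected: transcribing forms not yet entered, going back to women about their answers, and settling analysis choices that the plan leaves open. The team states in its Introduction and Background that it expects Kenalog to prove efficacious, so there is a direction in which unmasked judgement could lean. What is at stake is the credibility of data handling and secondary analyses after the last visit, not the validity of the answers as the women gave them.

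**Working it through.** **1. The plan's own figure.** Sample size gives a difference of 4.03, SD 5.6, two-sided alpha 0.05 and power 80%. The two-sample t-test solution is 31.3 per group, rounded up to 32. Allowing for 20% dropout, 64 / (1 − 0.20) = 80. Power at 32 per group is 80.9%. The stated sample size reproduces and is not in question; moving the opening of the code changes neither N, power nor alpha.

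**2. What is settled, and what may be open, when the last patient finishes.**

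| Item | Section | Settled by then? |
|---|---|---|
| Women's O'Leary-Sant answers at week 6 | Data collection methods | Yes: on paper, given blind |
| Primary test (two-sided t-test on the 6-week score, by assigned group) | Sample size; Data Analysis and Statistical Methods | Yes |
| Entry of paper forms | Data Handling/Storage | Not necessarily: no deadline |
| Clarification of answers | Confidentiality | Not necessarily: no cut-off |
| Regression cofactors | Data Analysis and Statistical Methods | No: examples only |
| Database lock, masked arm codes | none | Not mentioned |

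**3. Volume.** The ceiling is 80 women × 3 time points × 6 instruments = 1,440 forms, of which at most 80 are week-6 O'Leary-Sant forms. This is not the exposure. Dropout lowers it, and recruitment runs from January 2019 to July 2020, so forms may be entered along the way. The relevant number is the backlog at the last visit, which the documents do not give.

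**4. Size, as an assumption only.** Suppose a share of one arm's week-6 scores is moved in one direction. The documents support neither the share nor the size of the move.

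- Standard error of the difference = 5.6 × √(2/32) = 1.40.
- Bias = share × shift. Low: 0.10 × 1 = 0.10 points. Middle: 0.175 × 2 = 0.35. High: 0.25 × 3 = 0.75.
- Against the 4.03-point target: 0.10 / 4.03 = 2.5%; 0.75 / 4.03 = 18.6%.
- Two-sided rejection probability with no true effect (noncentral t, 62 degrees of freedom, noncentrality = bias / 1.40): 5.06% at 0.10, 5.35% at 0.25, about 5.7% at 0.35, 6.43% at 0.50 and 8.24% at 0.75.

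The low end is negligible, and only the most extreme combination reaches 8.2%.

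**5. The adverse-event exception.** Read literally, Interventions lets an adverse event open the sequence itself. Unblinding (unmasking) discloses only the affected participant's group. The two sections need to be reconciled.

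**6. Per-protocol set.** Data Analysis and Statistical Methods states the minimum of 4 instillations for the Kenalog arm only. Membership as written therefore cannot be determined without knowing the arms, but its definition can be fixed beforehand.

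**The case against.** The strongest reply is that this is an unspecified safeguard and not a planned unblinding. The rule is a floor: it says when the code may not be opened, and does not schedule opening before entry is complete. Blinding (masking) states the investigators' masking without an end date. Harms provides for monthly review of data quality and management, so entry need not wait until the end. The primary t-test does not depend on the cofactor regression. All of this stands, and it keeps the point small. It does not remove it, because the only sentence that gives an end to the concealment gives one that can precede the completion of entry and clarification.

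Three stronger readings are tempting, and the documents do not support them.

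- A reader might infer that the double blind is undermined for a self-reported primary outcome. Under the planned rule, every original answer is written by a blinded woman before the code may be opened, so self-report on paper limits the exposure.
- A reader might infer that any resulting bias would be undetectable. The paper forms are kept in a locked cabinet, so transcription changes can be found by comparison for as long as the forms are held, and auditing is open to the IRB. A changed answer after clarification, or a model choice, is harder to trace.
- A reader might infer that the analysing biostatistician is the one who holds the allocation. The plan does not say so, and does not say that they differ.

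**Conclusion.** The point holds, at minor severity. Opening of the sequence is tied to the last patient and not to a lock, and no other section closes the gap. What is left unprotected is entry of the remaining forms, later clarification of answers, and secondary analysis choices. Blinding during outcome collection, the primary test and the sample size are unaffected.

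The size of any bias cannot be derived from the documents. The 5.1% to 8.2% range rests wholly on assumed shares and shifts, all in one direction, and serves only to show what would have to happen for the gap to matter. The conclusion also assumes that some entry or clarification is still outstanding at the last visit, which the plan permits but does not state.

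**What to change.** Change the rule in Interventions so that the sequence is opened only after:

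1. all questionnaires are entered and checked, and clarifications with women are closed;
2. the definitions of the analysis sets and the list of regression cofactors are fixed in writing;
3. the database is locked. REDCap is already one of the permitted databases and can be used for this.

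For the per-protocol set, fix the definition and not the membership before opening, given the Kenalog-only threshold.

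Give the analyst arms coded A/B for the primary analysis, and state whether the analyst is a different person from the biostatistician who made the sequence, since coding protects nothing if they are the same. Align the adverse-event exception in Interventions with Unblinding (unmasking), which discloses only the affected participant's group.

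The cost is a short text amendment, the work of closing and locking the data, and a short delay between the last visit and unblinding. No patients or visits are added, and power and alpha are unchanged.

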2. Change in O'Leary-Sant total scores and subscores (problem and symptom indices scores) from baseline to last collected measure
3. Pelvic pain and urgency/frequency (PUF) questionnaire [18]
4. Overactive Bladder Questionnaire (OABq) [19]
5. Pelvic floor distress inventory (PFDI) [20]
6. Sexual function measured by the Pelvic Organ Prolapse Incontinence Sexual Questionnaire, IUGA-Revised (PISQ-IR) questionnaire [21-23]
7. Visual Analogue Scale (VAS) for pain as measured on marking on 10-centimeter (cm) ruler (measured in cm, 0= no pain and 10= most severe pain possible)
8. Prevalence and nature of adverse events related to study medications
9. The prevalence of notable OAB symptoms in the study population and in the different study groups, as defined by OABq score ≥ 8
10. The prevalence of concurrent pain or irritative organ disorders (irritable bowel syndrome, fibromyalgia, chronic pain, chronic pelvic pain, vulvodynia, anxiety, depression, chronic fatigue syndrome) in the study population and in the different study groups
11. Perform cost-analysis of two treatment groups

Participant timeline:

Upon recruitment, women will complete questionnaires (Figure 1) about their characteristics and health history, presence or absence and number of other pain syndromes related to IC/BPS (irritable bowel syndrome, fibromyalgia, chronic pain, chronic pelvic pain, vulvodynia, anxiety, depression, chronic fatigue syndrome), and complete the following reliable, validated questionnaires as follows:

- (1) O'Leary-Sant questionnaire (problem and symptom index scores) [16,17]
- (2) Pelvic pain and urgency/frequency (PUF) questionnaire [18]
- (3) Overactive Bladder Questionnaire (OABq) [19]
- (4) Pelvic floor distress inventory (PFDI) [20]
- (5) Sexual function measured by the Pelvic Organ Prolapse Incontinence Sexual Questionnaire, IUGA-Revised (PISQ-IR) questionnaire [21-23]
- (6) Visual Analogue Scale (VAS) for pain as measured on marking on 10-centimeter (cm) ruler (measured in cm, 0= no pain and 10= most severe pain possible)

Study Title: Randomized controlled trial comparing two different bladder instillation treatments for interstitial cystitis/bladder pain syndrome.

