Bladder instillation will be performed weekly with the same mixture that the patient was randomized to (mixture with or without Kenalog) and for 6 weeks. Symptom questionnaires will be given at baseline, 3 weeks, and 6 weeks of treatment. If the patient misses a study appointment, she will be called by telephone and queried about side effects and if appropriate, re-scheduled for an appointment.

We plan to recruit patients from January 2019 until July 2020. Patient follow up will be completed by September 2020. As bladder instillations are commonly performed and considered low risk, no interim analysis will be performed. Urinary tract infection will not be considered an adverse event related to study drug but will be monitored in data collection.

Sample size

Sample size calculation was based on the primary outcome, the O'Leary-Sant score on the final day of bladder instillation treatment as compared between the two treatment groups. Based on previous studies, patients have a baseline IC/BPS score following standard medical treatment of approximately 24 ± 5.6 points.[16,17] A 4.03 point decrease from baseline on the O'Leary-Sant questionnaire corresponds with at least a 50% perceived improvement in the patient's disease.[24] We believe this level of difference between the groups in the final O'Leary-Sant scores would be clinically significant. We want 80% power to detect a 4.03 point decrease from a baseline mean score of 24 (expected score in the bladder instillation without Kenalog group after treatment) with a standard deviation ≤ 5.6 points (alpha 0.05) with a 2-sided t-test. The G*Power sample size calculator was used for the power calculations (<https://www.stat.ubc.ca/~rollin/stats/ssize/n2.html>) and these calculations were confirmed for accuracy by a University of Louisville biostatistician. The resulting sample size was $n= 32$ for each group for a total of 64 enrolled patients. Accounting for a 20% dropout in the study, this would translate to a sample size of 80 patients enrolled with a goal of 40 per group.

Recruitment

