- (1) Imputation of missing data with assumption of treatment non-response (baseline O'Leary-Sant and other outcomes scores carried forward as the final outcome)
- (2) Imputation of missing data with assumption of “best last known” response (final outcomes assumed to be the best value for that outcome during the study course that was available)
- (3) Imputation of missing data with “most recent last known” response (final outcomes assumed to be the most recent value for that outcome during the study course that was available)

Planned secondary analyses will include: (1) treatment response of subgroups of patients with and without prominent OAB symptoms (OABq score ≥ 8); (2) treatment response in patients with and without a history of prior IC/BPS treatment; and (3) the relationship between known coexisting pain and irritative organ disorders (irritable bowel syndrome, fibromyalgia, chronic pain, chronic pelvic pain, vulvodynia, anxiety, depression, chronic fatigue syndrome) and response to treatment; (4) Treatment cost-analysis. The interaction of these factors (prominent OAB symptoms, prior IC/BPS treatment, coexisting pain or irritative organ disorders) with the relationship between randomization and treatment response will be determined.

Potential Benefits:

Participants may benefit from the multiple agents in the bladder instillation, including Kenalog, a steroid. Steroids have been shown to be helpful in patients with IC/BPS. Bladder instillation therapy is a well-tolerated and commonly used treatment of IC/BPS.

Potential Risks:

This research study cannot practically be conducted without access and use of protected health information. Thus, the principle risk to patients involved in the study is a potential breach of confidentiality and misuse or exposure of this information. With this in mind, the investigators will conduct all research activities in such a way that maximizes data security and minimizes any risk of potential data breaches.

Patients may have risk of embarrassment or offense due to the private and personal nature of some of the study questions (e.g. such as questions about urinary incontinence or sexual activity). This risk will be minimized by accurate description of the nature of the study and the study outcomes to the patient prior to informed consent, and communication with the patient regarding the right to decline to answer any given study question.

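### Secondary outcome 2 runs to each woman's last available O'Leary-Sant score instead of week 6, which builds last-value-carried-forward into the endpoint and conflicts with the analysis section

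*Combined protocol and SAP*

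**What the plan says.** The Outcomes section sets two post-baseline collection points: "All outcome measures will be collected at 3 weeks into the bladder instillation schedule and again at the completion of the bladder instillations", the latter at week 6. The Participant timeline agrees: "Symptom questionnaires will be given at baseline, 3 weeks, and 6 weeks of treatment".

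The primary outcome is the O'Leary-Sant score "as compared between study groups at completion of the bladder instillations", and secondary outcome 1 (the two index scores) is also fixed at the end of treatment. Secondary outcome 2, the change in total and index scores, is instead taken "from baseline to last collected measure", with no visit named.

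The Data Analysis and Statistical Methods section adds three relevant statements:
- The initial intention-to-treat analysis is described as "comparing women who followed up at the completion of the study (6-week outcomes) between the study groups".
- Changes over time are assigned to paired t-tests, with the example "change from baseline to 8-week O'Leary-Sant score".
- The third sensitivity analysis replaces missing data by the most recent value: "final outcomes assumed to be the most recent value for that outcome during the study course that was available".

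Under Interventions, early stopping is allowed: "If patients have a reaction to the bladder instillation or desire to stop the instillations, they may do so". The Sample size section allows for 20% dropout, giving 80 women enrolled.

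**The concern.** The trial's hypothesis is that symptoms improve more with Kenalog, and secondary outcome 2 is the only listed outcome explicitly defined as a change. It will be read beside the primary result. As worded, its value depends on when a woman was last measured as well as on her treatment: some changes would follow about three weekly instillations and others six.

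Early stopping is likely to mean no week-6 score. Final questionnaires are tied to the sixth instillation and handed in at appointments. The telephone call after a missed appointment asks about side effects and rescheduling; no symptom score by telephone is described.

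Two consequences follow. If part of the effect appears after week 3, equal dropout dilutes a real difference. If dropout differs between arms, a difference can appear where none exists. In addition, the final-score and change-score results could describe different women at different times.

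**Working it through.** **Step 1. The plan's own figure.** Inputs from the Sample size section: difference 4.03, SD 5.6, two-sided alpha 0.05, power 80%, dropout 20%.
- Normal approximation: n per group = 2 × (1.96 + 0.842)² × 5.6² / 4.03² = 30.3, rounded up to 31.
- Two-sample t-test: 31.3, rounded up to 32, as stated.
- Dropout: 64 / (1 − 0.20) = 80, as stated.

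This calculation concerns the final score. The documents give no power figure for the change score.

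**Step 2. Time points for change, side by side.**

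| Place | End point |
|---|---|
| Secondary outcome 2 | last score available |
| Initial analysis, Data Analysis section | 6 weeks |
| Example of a change, Data Analysis section | 8 weeks |
| Planned questionnaires, Participant timeline | baseline, 3 and 6 weeks only |

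The first three do not agree, and the third has no planned visit.

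**Step 3. How many women.** 20% of 80 = 16 women could lack a week-6 score.

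**Step 4. Equal dropout, real effect.** Let D be the true week-6 difference, d the dropout in each arm, and f the share of the effect present at week 3. Assume that every dropout has a week-3 form and would otherwise have followed the course of her arm. Then

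measured difference = D × [(1 − d) + d × f].

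D = 4.03 and d = 0.20 come from the plan; f is an assumption.
- f = 0.25: 4.03 × (0.80 + 0.05) = 3.43
- f = 0.50: 4.03 × (0.80 + 0.10) = 3.63
- f = 1: 4.03 × (0.80 + 0.20) = 4.03

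**Step 5. Unequal dropout, no true difference.** Both arms improve by C at week 6 and by f × C at week 3, with dropout d₁ and d₂:

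false difference = C × (1 − f) × (d₂ − d₁).

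Assume dropout of 10% and 30% (4 + 12 = 16 of 80, still 20% overall) and f = 0.5.
- C = 4.03: 4.03 × 0.5 × 0.20 = 0.40
- C = 8.06: 8.06 × 0.5 × 0.20 = 0.81

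The arm that loses fewer women looks better. If d₁ = d₂, the result is 0 whatever C and f are.

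**Step 6. Scale.** If the planning SD of 5.6 also held for change scores (an assumption), the standard error of a difference with 40 per arm is 5.6 × √(2/40) = 1.25. The false difference is then about one third (0.40 / 1.25) to two thirds (0.81 / 1.25) of a standard error.

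**The case against.** The strongest reply is that the Data Analysis section already limits the initial analysis to women seen at 6 weeks. If that set governs every outcome, each last score is a week-6 score and nothing is mixed. This is possible, but the plan does not say so. It would also leave the wording of secondary outcome 2 without purpose. The two places conflict, and neither clearly overrides the other.

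A second reply is that a completer analysis at week 6 is not free of bias either: it loses up to 16 of 80 women and is distorted if dropout depends on response. This stands. It is a reason to prefer a model that uses both visits, not a reason to leave the time point open.

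Third, the change scores are assigned to paired t-tests, which compare visits within an arm. No between-arm test of change is named, so the effect on the treatment comparison arises only once the arms are compared on this outcome. That also stands.

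Fourth, the week-3 effect, the improvement in each arm and the dropout imbalance are all assumed. The documents give only 20% dropout overall.

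A reader might also infer that a woman with no form after baseline counts as a change of zero. The documents do not say this for secondary outcome 2. Carrying baseline forward is stated only in the first sensitivity analysis, and such a woman may simply have no value.

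**Conclusion.** The point holds as a defect in the definition of one secondary outcome. Its wording lets a week-3 change stand in for a week-6 change, and the plan contains three incompatible end points for change.

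The size is modest and conditional. Dilution runs from none to 0.60 points (4.03 − 3.43) over the week-3 shares examined, at 20% dropout with week-3 forms for all dropouts. A false difference of about 0.4 to 0.8 points needs both an imbalance such as 10% versus 30% and improvement that continues after week 3. Nothing in the plan predicts that imbalance, and with equal dropout and no true effect there is no false difference.

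A reader might infer that the main result is compromised. It is not: the primary outcome is fixed at the end of treatment, and the sample size was calculated on that score and reproduces.

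**What to change.** - Define secondary outcome 2 as change from baseline to the 6-week assessment, for the total and both indices. Report change to week 3 separately.
- Correct the 8-week example in the Data Analysis section to 6 weeks.
- Compare arms with a baseline-adjusted model in place of within-arm paired t-tests. A mixed model using weeks 3 and 6 is preferable, because women with only a week-3 form still contribute without that score being treated as a week-6 result. It assumes that data are missing at random given the observed scores.
- Keep the last-value version only as the third sensitivity analysis, and say how women with no post-baseline form are handled.

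The cost is wording and slightly more analysis work, with no extra women, visits or forms. If a completer-only analysis were chosen instead, women without a week-6 form would drop out of the change analysis, as they already do from the initial analysis of the primary outcome.
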